8.1 Visit procedures

The following sections describe the assessments and procedures. Timing of the assessments at specific visits and visit windows are defined in the flow chart (see section [2](#)).

Informed consent must be obtained at least one day before any trial related activity, see section [18.2](#).

The investigator must keep a subject screening log, a subject identification code list and a subject enrolment log. Only subjects who have signed the informed consent form should be included on the logs. The subject screening log and subject enrolment log may be combined in one log.

At the first visit the subjects will be provided with information regarding the trial and asked to sign the informed consent form. At the screening visit, subjects will be provided with a subject ID card stating that they are participating in a trial and giving contact addresses and telephone numbers of relevant trial site staff. Subjects should be instructed to return the card to the investigator at the last trial visit or to destroy the card after the last visit.

Each subject will be assigned a unique 6-digit subject number which will remain the same throughout the trial. A screening session must be performed in the IWRS.

Screening failures: For screening failures the screening failure form in the electronic case report form (eCRF) must be completed with the reason for not continuing in the trial. Serious and non-serious adverse events from screening failures must be transcribed by the investigator into the eCRF. Follow-up on serious adverse events (SAEs) must be carried out according to Section [12](#).

A screening failure session must be made in the IWRS. The case book must be signed in the eCRF.

Re-screening is NOT allowed if the subject has failed one of the inclusion or exclusion criteria; this includes re-sampling if the subject has failed one of the inclusion or exclusion criteria related to laboratory parameters. Re-screening of subjects is allowed ONLY if the screening window of 21 days between screening visit and randomisation visit is exceeded (e.g. due to unforeseen or urgent events which make it impossible for the subject to attend the planned randomisation visit), and ONLY if the subject was eligible for randomisation. No separate informed consent is required, but all assessments and lab samples must be repeated.

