8.2.2 Concomitant illness and medical history

A **concomitant illness** is any illness that is present at the start of the trial (i.e. at screening visit) or found as a result of a screening procedure or other trial procedures performed before exposure to trial product.

Medical history is a medical event that the subject has experienced in the past.

The information collected for concomitant illness and medical history should include diagnosis, date of onset and date of resolution or continuation, as applicable.

Any change to a concomitant illness should be recorded during the trial. A clinically significant worsening of a concomitant illness must be reported as an AE.

The following assessments must be recorded in the eCRF:

- History of GHD:
 - Childhood onset (CO): Idiopathic or organic
 - Adulthood onset (AO)
- Concomitant illnesses present at start of the trial
- Relevant medical conditions/illnesses in the past, including history of cancer/intracranial tumour
- Treatment for GHD during the 6 months prior to screening, including type of medication and dose
- Other hormone replacement therapy

The method used for diagnosing GHD should be recorded in the eCRF. The method must be in accordance with the “Guidance of diagnostic criteria and treatment for AGHD (Age \geq 18): 2013 (Japanese)”, or relevant guidelines applicable at the time of GHD diagnosis.

It must be possible to verify the subject’s medical history in source documents such as subject’s medical record. If a subject is not from the investigator’s own practice, the investigator must make reasonable effort to obtain a copy of the subject’s medical record from the relevant party, e.g. primary physician. The investigator must document any attempt to obtain external medical information by noting the date(s) when information was requested and who has been contacted.

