12.1 Definitions

12.1.1 Adverse event

An adverse event (AE) is, according to GCP definition, any untoward medical occurrence in a subject administered a medicinal product, and which does not necessarily have a causal relationship with this treatment.

An AE can therefore be any unfavourable and unintended sign (including an abnormal laboratory finding), symptom or disease temporally associated with the use of a product, whether or not considered related to the product.

An AE includes:

- A clinically significant worsening of a concomitant illness.
- A clinical laboratory adverse event (CLAE): a clinical laboratory abnormality which is clinically significant, i.e. an abnormality that suggests a disease and/or organ toxicity and is of a severity that requires active management. Active management includes active treatment or further investigations, for example change of medicine dose or more frequent follow-up due to the abnormality.

The following should **not** be reported as AEs:

- Pre-existing conditions, including those found as a result of screening or other trial procedures performed before exposure to trial product (pre-existing conditions should be reported as medical history or concomitant illness).
- Pre-planned procedures unless the condition for which the procedure was planned has worsened from the first trial related activity after the subject has signed the informed consent.

The following three definitions are used when assessing an AE:

- **Severity**
 - **Mild** – no or transient symptoms, no interference with the subject's daily activities.
 - **Moderate** – marked symptoms, moderate interference with the subject's daily activities.
 - **Severe** – considerable interference with the subject's daily activities; unacceptable.
- **Causality**

Relationship between an AE and the relevant trial product(s):

 - **Probable** - Good reason and sufficient documentation to assume a causal relationship.
 - **Possible** - A causal relationship is conceivable and cannot be dismissed.
 - **Unlikely** - The event is most likely related to aetiology other than the trial product.

- **Final outcome**

- **Recovered/resolved** - The subject has fully recovered, or by medical or surgical treatment the condition has returned to the level observed at the first trial-related activity after the subject signed the informed consent.

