12.2 Reporting of adverse events

All events meeting the definition of an AE must be collected and reported. This includes events from the first trial-related activity after the subject has signed the informed consent until the end of the post-treatment follow-up period (week 53). The events must be recorded in the applicable eCRF forms in a timely manner, see timelines below and [Figure 12-1](#).

During each contact with the trial site staff, the subject must be asked about AEs and technical complaints, for example by asking: “Have you experienced any problems since the last contact?”

All AEs, either observed by the investigator or the subject, must be reported by the investigator and evaluated.

All AEs must be recorded by the investigator on an AE form. The investigator should report the diagnosis, if available. If no diagnosis is available, the investigator should record each sign and symptom as individual AEs using separate AE forms.

For SAEs, a safety information form must be completed in addition to the AE form. If several symptoms or diagnoses occur as part of the same clinical picture, one safety information form can be used to describe all the SAEs.

For all non-serious AEs, the applicable forms should be signed when the event is resolved or at the end of the trial at the latest.

Timelines for initial reporting of AEs:

The investigator must complete the following forms in the eCRF within the specified timelines:

[figure not shown]
- **SAEs:** The AE form **within 24 hours** and the safety information form **within 5 calendar days** of the investigator's first knowledge of the SAE.

Both forms must be signed within 7 calendar days from the date the information was entered in the eCRF.

For SAEs requiring reporting on a specific event form (medication error form and injection site reaction form): In addition to the above the specific event form within **14 calendar days** from the investigator's first knowledge of the AE.

If the eCRF is unavailable, the concerned AE information must be reported on a paper AE form and sent to Novo Nordisk by fax, e-mail or courier within the same timelines as stated above. When the eCRF becomes available again, the investigator must enter the information on the form into the eCRF.

Contact details (fax, telephone, e-mail and address) are provided in the investigator trial master file.

Timelines are for the completion of forms from the time of investigator's awareness.

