12.3 Follow-up of adverse events

The investigator must record follow-up information by updating the forms in the eCRF. Follow-up information must be reported to Novo Nordisk according to the following:

- **SAEs:** All SAEs must be followed until the outcome of the event is “recovered/resolved”, “recovered/resolved with sequelae” or “fatal”, and until all queries have been resolved. Cases of chronic conditions, cancer or AEs ongoing at time of death (where death is due to another AE) may be closed with the outcome “recovering/resolving” or “not recovered/not resolved”. Cases can be closed with the outcome of “recovering/resolving” when the subject has completed the follow-up period and is expected by the investigator to recover.

The SAE follow-up information should only include new (e.g. corrections or additional) information and must be reported **within 24 hours** of the investigator’s first knowledge of the

information. This is also the case for previously non-serious AEs which subsequently become SAEs.

- **Non-serious AEs:** Non-serious AEs must be followed until the outcome of the event is “recovering/resolving”, “recovered/resolved” or “recovered/resolved with sequelae” or until the end of the follow-up period stated in the protocol, whichever comes first, and until all queries related to these AEs have been resolved. Cases of chronic conditions, cancer or AEs ongoing at time of death (where death is due to another AE) may be closed with the outcome “recovering/resolving” or “not recovered/not resolved”. Cases can be closed with the outcome of “recovering/resolving” when the subject has completed the follow-up period and is expected by the investigator to recover.

The investigator must ensure that the recording of the worst case severity and seriousness of an event is kept throughout the trial. A worsening of an unresolved AE must be reported as follow up with re-assessment of severity and/or seriousness of the event.

Queries or follow-up requests from Novo Nordisk must be responded to **within 14 calendar days** from the date of receipt of the request, unless otherwise specified in the follow-up request.

SAEs after end of trial: If the investigator becomes aware of an SAE with a suspected causal relationship to the investigational medicinal product occurring to a subject after the subject has ended the trial, the investigator should report this SAE within the same timelines as for SAEs during the trial.

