17.3 Primary endpoint

- Incidence of adverse events, including injection site reactions, from first administration of trial product to end of the trial period (53 weeks including follow-up)

The primary objective of the trial is to evaluate the safety of once weekly dosing of somapacitan during 52 weeks of treatment in Japanese GHD subjects previously treated with hGH and analysis of AEs will be the primary tool for achieving this. AEs will be analysed using descriptive statistics. All AEs with onset after the first administration of trial product and up until end of the trial (53 weeks) or 14 days after last trial drug administration, whichever comes first, will be included in the analysis. The AEs will be summarised by treatment, MedDRA (Medical Dictionary for Regulatory Activities) system organ class and MedDRA preferred term. The descriptive statistics will include the number and percentage of subjects who experienced AEs, the number of events and rate per 100 person years. AEs will be listed by treatment and subject with information on severity, relationship to trial product and demographics. AEs with onset before first dosing will be reported in a separate listing. AEs with onset 14 days or more after last trial drug administration will be reported in a separate listing.

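### An adverse event that begins between screening and first dose and worsens on trial drug is left out of the primary AE tables

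*Combined protocol and SAP*

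**What the plan says.** Four rules in the protocol bear on this.

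- **Start of collection (12.2).** AE reporting covers "events from the first trial-related activity after the subject has signed the informed consent" up to the end of follow-up at week 53. Under 8.1, consent comes at least one day before any such activity. The flow chart puts screening 2 to 3 weeks before randomisation, and 8.1 gives a "screening window of 21 days between screening visit and randomisation visit". The first dose is taken at randomisation (5.3).
- **Worsening of an open AE (12.3).** "A worsening of an unresolved AE must be reported as follow up with re-assessment of severity and/or seriousness of the event". The worst severity and seriousness are kept on the record. No exception is made for an AE that began before first dose.
- **What the primary analysis counts (17.3).** It takes "All AEs with onset after the first administration of trial product and up until end of the trial (53 weeks"), or up to 14 days after the last dose if that is earlier. For the rest, "AEs with onset before first dosing will be reported in a separate listing".
- **Concomitant illness (8.2.2, 12.1.1).** "Pre-existing conditions, including those found as a result of screening or other trial procedures performed before exposure to trial product" are not AEs but medical history or concomitant illness. For the latter, "A clinically significant worsening of a concomitant illness must be reported as an AE".

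Section 17 allows a SAP if one proves necessary. The text supplied contains no separate definition of a treatment-emergent event.

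**The concern.** In a safety trial, a symptom that was mild before exposure and becomes severe or serious on drug would normally be treated as emerging on treatment. Here the recording rule holds the onset date before first dose, and the analysis rule selects on onset date alone. The two combined exclude the on-drug change.

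The population makes this relevant. Subjects enter on daily hGH, so an event arising in the screening window may be of a kind that 12.6 associates with growth hormone, such as oedema or joint pain. They then switch to a dose that is titrated from a start expected to lie below maintenance for most subjects (5.3.3). An earlier somapacitan trial described in 3.1.4 saw both the frequency and the severity of AEs rise with dose. A change in severity after the switch is part of what the primary objective is meant to capture, and 17.3 makes the AE analysis the main means of meeting that objective.

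**Working it through.** The plan gives no figure to reproduce: the AE analysis is descriptive and the sample size rests on no formal calculation (17.1). The check is therefore a tracing of the rules, followed by arithmetic for scale only.

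**Tracing one event.** Suppose a subject reports mild joint pain one week after screening, it is still present at first dose, and it becomes severe in week 10.

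1. It began after the first trial activity, so 12.2 makes it reportable as an AE, with onset before first dose.
2. It is unresolved when it worsens, so 12.3 makes the worsening follow-up of the same AE. Severity is updated; onset is not.
3. Its onset is not after the first administration, so 17.3 places it in the separate listing and outside the tables by treatment, system organ class and preferred term.

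**Three variants that are not caught.**

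- The pain was present at screening, or was found by a trial procedure before exposure: it is a concomitant illness, and its clinically significant worsening is an AE that can carry a post-dose onset.
- The pain resolved before dosing and came back later: the follow-up rule covers unresolved AEs only.
- The pain persisted without worsening: there is no on-drug change to count.

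**Inputs.** 60 subjects, 45 and 15 by arm (17.1); a window of 14 to 21 days (flow chart, 8.1). *Assumed, because the documents give no values:* 1 to 4 AEs per person-year before dosing, and 2% to 10% of those both open at first dose and worsening on drug. The second range corresponds, for example, to 20% to 40% unresolved and 10% to 25% of those worsening: 0.20 × 0.10 = 2% and 0.40 × 0.25 = 10%.

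**Expected number omitted** = subjects × days/365.25 × rate × proportion.

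- Pre-dose time: 60 × 14/365.25 = 2.3 and 60 × 21/365.25 = 3.4 person-years. Time over 53 weeks: 60 × 371/365.25 = 60.9 person-years.
- Low: 2.30 × 1 × 0.02 = 0.05 events.
- High: 3.45 × 4 × 0.10 = 1.4 events.
- By arm, on the same inputs: 0.03 to 1.03 on somapacitan and 0.01 to 0.34 on Norditropin.

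**Effect of one omitted subject.**

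- On one preferred-term row, at most 1/45 = 2.2 points or 1/15 = 6.7 points.
- On the percentage with any AE, there is an effect only if the subject has no other counted AE. With a constant rate over 371/365.25 = 1.016 years, the Poisson probability of none is exp(−1.016 × rate): 36% at 1 per person-year, 13% at 2 and 2% at 4.

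**The case against.** The strongest reply is that little falls into the gap and that nothing in it goes unreported.

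- **Reach.** A reader might infer that anything starting the day after screening is unprotected. The documents do not support that. The definition of concomitant illness extends to conditions found by trial procedures before exposure, and physical examination and vital signs are scheduled at randomisation. Sections 8.4.2 to 8.4.4 also call for AE recording when ECG (if abnormal and clinically significant), physical findings or vital signs (if clinically significant) worsen after screening. What remains is mainly subject-reported events in the window. This limit stands.
- **Reporting.** A reader might infer that a serious worsening disappears. It does not: 12.3 keeps the worst severity and seriousness and requires reporting within 24 hours when a non-serious AE becomes serious, and the event is still listed. A reader might also infer that the listing would present on-drug severity as if it had arisen before exposure. Neither the layout of the listing nor the follow-up fields of the eCRF are visible, so that cannot be claimed.
- **Convention.** Counting by onset is a coherent reading of incidence, and the endpoint carries no test or margin. But the protocol itself treats the on-drug worsening of a concomitant illness as an AE, so similar worsenings are counted or not according to how the condition was first filed.
- **A later SAP.** It could change the counting rule. Section 17 makes a SAP optional, however, and a rule based on worsening needs a date of worsening that the visible text does not ask for.

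None of this removes the gap for an open AE with onset before first dose.

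**Conclusion.** The gap is real and follows from stated rules, not from missing detail: 12.3 and 17.3, applied as written, leave an on-drug worsening of a pre-dose AE out of the primary tables, even when it becomes serious, and no other section restores it. It is confined to events recorded as AEs in the 14 to 21 days before first dose that are still unresolved at dosing.

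The size is small, roughly 0 to 1.5 events in the trial, and that range depends wholly on assumed rates. The 2.2 and 6.7 points are maxima for a single preferred-term row. It would be wrong to read them as the likely shift in overall AE incidence, which would usually not change. The reason to act is that the classification is wrong for the primary endpoint and cheap to correct, and that the rare case most worth tabulating, a worsening to serious, is among those omitted. The rule tracing is firm; the expected count is not.

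**What to change.** - **17.3:** include every AE with onset, or with worsening in severity or seriousness, after the first administration and within the existing end limits. State that each such event is counted once.
- **12.3:** require the date of worsening to be recorded for any AE with onset before first dose. This can be done on the follow-up entry or by opening a new AE dated at the worsening. If the second route is chosen, exempt this case from the follow-up rule and link the two records so that the event is not counted twice.

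The cost is one date field with an eCRF completion instruction, and possibly a small rise in AE counts. It is best settled before data collection, since dates of worsening may be hard to reconstruct afterwards. Treatment and expedited reporting are unaffected.

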17.4 Secondary endpoints

17.4.1 Supportive secondary endpoints

17.4.1.1 Efficacy endpoints

- Change from baseline (randomisation) to end of treatment period (52 weeks) in:
 - cross-sectional total adipose tissue compartments (TAT),
 - subcutaneous adipose tissue compartments (SAT), and
 - intra-abdominal or visceral adipose tissue compartments (VAT)

determined by quantitative computed tomography (CT) scans

The change in abdominal adipose tissue compartments (TAT, SAT and VAT) from baseline to week 52 endpoints will be used to address the second objective of evaluating the efficacy of once weekly dosing of somapacitan by measuring the effect on abdominal adipose tissue during 52 weeks of treatment in Japanese GHD subjects previously treated with hGH.

Changes in abdominal adipose tissue compartments (TAT, SAT and VAT) from baseline to week 52 will be analysed using an analysis of covariance (ANCOVA) model with treatment, GHD onset type and sex as factors and baseline value as a covariate. From the model the treatment difference at week 52 between somapacitan and Norditropin[®] FlexPro[®] will be estimated and the corresponding 95% confidence interval and p-value will be calculated for each endpoint. Subjects without week 52 data for the analysed endpoint will not be included in the analysis. It is expected that less than 7% of the subjects will not have week 52 data for the CT scan based endpoints.

- Change from baseline (randomisation) to end of treatment period (52 weeks) in Treatment Satisfaction Questionnaire for Medication (TSQM-9) scores for:
 - effectiveness
 - convenience

- global satisfaction

The change from baseline (randomisation) to end of treatment period (52 weeks) in Treatment Satisfaction Questionnaire for Medication (TSQM-9) scores will be used to address the second objective of evaluating the degree of treatment satisfaction of once weekly dosing of somapacitan during 52 weeks of treatment in GHD subjects previously treated with daily hGH.

The change in TSQM-9 scores (effectiveness, convenience and global satisfaction scores) at 32 and 52 week's measurements will be analysed using a mixed model for repeated measurements (MMRM), with treatment, GHD onset type and sex as factors and baseline as a covariate, all nested within week as a factor. An unstructured covariance matrix will be used to describe the variability for the repeated measurements for a subject. From the MMRM the treatment differences at end of treatment period (52 weeks) between somapacitan and Norditropin[®] FlexPro[®] will be estimated and the corresponding 95% CI and p-value will be calculated for each endpoint. Subjects without post-randomisation data for the analysed endpoint will not be included in the analysis.

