5.4 Treatment after discontinuation of trial product

No treatment will be offered after end of trial. When discontinuing trial products, either after the follow-up visit (week 53) or if trial product is discontinued prematurely, the subject should be switched to a suitable marketed product at the discretion of the investigator.

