6.4 Criteria for premature discontinuation of trial product

Efforts must be made so that subjects attend and complete all scheduled visit procedures. Subjects should stay in the trial irrespective of lack of adherence to randomised treatment, lack of adherence to visit schedule or missing assessments. Only subjects who decline any further contact with the site in relation to the trial will be considered as withdrawn from the trial (see section [6.5](#)).

The subject may be prematurely discontinued from trial product at the discretion of the investigator due to a safety concern or if judged non-compliant with trial procedures.

The subject must be prematurely discontinued from trial product if the following applies:

1. Included in the trial in violation of the inclusion and/or exclusion criteria
2. Pregnancy
3. Intention of becoming pregnant
4. Simultaneous participation in another clinical trial of an approved or non-approved investigational medicinal product.
5. AE: If a subject reports symptoms which are considered unacceptable by the subject or the investigator, regardless of relationship to trial product, treatment must be discontinued
6. If physicians definitely diagnose diabetes mellitus in accordance with diagnostic criteria established by the Japan Diabetes Society²¹ during the course of the trial the subject should be discontinued from treatment

See Section [8.1](#) for procedures to be performed for subjects discontinuing trial product prematurely.

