Re-sampling of screening parameters is ONLY allowed during an unscheduled visit (see section [8.8](#)) if samples are lost or damaged before arriving at the analysing laboratory, or if the analysis failed at the laboratory.

Premature discontinuation of trial product: If a subject prematurely discontinues trial product, the investigator must undertake procedures similar to those for week 51+4 days as soon as possible, however, the subject should be encouraged to follow all remaining site visits in the trial according to the trial flow chart. The follow-up visit (week 53) must be performed at least two weeks after last administration of somapacitan and at least 8 days after last administration of Norditropin[®] FlexPro[®].

The primary reason for premature discontinuation of trial product must be specified in the end-of-treatment form in the eCRF, and final drug accountability must be performed. A treatment discontinuation session must be made in the IWRS.

Withdrawal from trial: If a subject withdraws consent, the investigator must aim to undertake procedures similar to those for week 51+4 days as soon as possible. If the subject agrees, the follow up visit (week 53) must be performed at least two weeks after last administration of somapacitan and at least 8 days after last administration of Norditropin[®] FlexPro[®].

The end-of-treatment form and the end-of-trial form must be completed, and final drug accountability must be performed even if the subject is not able to come to the trial site. A treatment discontinuation session must be made in the IWRS, and in the eCRF it must be specified that the subject will not participate in subsequent visits in the trial. The case book must be signed.

Although a subject is not obliged to give his/her reason(s) for withdrawing consent, the investigator must make a reasonable effort to ascertain the reason(s), while fully respecting the subject's rights. Where the reasons are obtained, the primary reason for withdrawing consent must be specified in the end-of-trial form in the eCRF system.

Review of diaries, patient reported outcomes (PROs), laboratory reports etc. must be documented either on the documents or in the subject's medical record.

If clarification of entries or discrepancies in the diary or patient reported outcomes is needed, the subject must be questioned and a conclusion made in the subject's medical record. Care must be taken not to bias the subject.

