8.3.2 Patient reported outcomes

Patient reported outcomes (PROs) will be assessed at randomisation and in week 32 and week 51 (see section 2) using the Treatment Satisfaction Questionnaire for Medication - 9 items (TSQM-9)²⁷. At randomisation, subjects will state their satisfaction with their pre-trial GH therapy, as they have not yet received trial medication.

The TSQM-9 is a generic questionnaire that measures a subject's satisfaction with medication. Items are rated on a 5- or 7-point scale according to the subject's experience with the medication and the concepts covered are satisfaction with the effect of the medication, convenience, confidence and global treatment satisfaction.

By using the TSQM-9 it will be possible to assess the subjects' satisfaction with medication.

The PRO questionnaire will be a self-administered questionnaire, to be completed by the subject without assistance of the site personnel. The questionnaire should be completed after all fasting related activities are completed but before any other trial related activity at each applicable visit. Written instructions on how to complete the questionnaire will be provided to the subject. Subjects who cannot complete the questionnaire themselves due to physical limitations may receive assistance with completion of the questionnaire. After completion the PRO must be reviewed by the investigator on the same day for potential AEs, including any overall change in health and concomitant medication. When reviewing the PRO questionnaire for AEs the investigator should not influence nor question the subject on the content of the subject's response to PRO questions. Review of the PRO must be documented either on the front page of the documents and/or in the subject's medical record. If clarification of entries in the PRO questionnaire is needed, the subject should be questioned and a conclusion made in the subject's medical record. Only the subject can make changes in the PRO. Care should be taken not to bias the subject. Filled in questionnaires will be sent for central data entry into the clinical database.

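### Do TSQM-9 scores given after an early stopper moves to a marketed product need their own rule in the MMRM?

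*Combined protocol and SAP*

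**What the plan says.** Section 5.4 provides that "if trial product is discontinued prematurely, the subject should be switched to a suitable marketed product at the discretion of the investigator". Section 6.4 keeps such subjects under follow-up: "Subjects should stay in the trial irrespective of lack of adherence to randomised treatment, lack of adherence to visit schedule or missing assessments". Section 8.1 adds that "the subject should be encouraged to follow all remaining site visits in the trial according to the trial flow chart", and that on stopping "the investigator must undertake procedures similar to those for week 51+4 days as soon as possible", which includes the questionnaire. Under 8.3.2 patient-reported outcomes "will be assessed at randomisation and in week 32 and week 51".

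Section 17.2 assigns efficacy data to the full analysis set by randomised arm. It requires any excluded subject or observation to be documented and signed off before database lock. The model in 17.4.1.1 covers "The change in TSQM-9 scores (effectiveness, convenience and global satisfaction scores) at 32 and 52" weeks, and its only data rule is "Subjects without post-randomisation data for the analysed endpoint will not be included in the analysis". Section 17.5 says that questionnaire results go into the clinical trial report. Section 17 allows a separate SAP, finalised before lock.

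**The concern.** TSQM-9 measures satisfaction with a medication, and the objective in 4.1 concerns once-weekly somapacitan. A somapacitan subject who stops, changes product and completes the week-51 questionnaire may be rating a daily injection, yet the score counts for somapacitan. Section 8.3.2 says which product is rated at randomisation (the pre-trial GH) but not which is rated after a switch. Section 17.3 limits adverse events to 14 days after last dose; TSQM-9 has no comparable limit. The discontinuation-visit score is collected, but 17.4.1.1 does not say how it is used.

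All three TSQM-9 scores are marked for public disclosure in 4.2.2.1. If switching were common, the published difference would mix satisfaction with somapacitan and satisfaction with whatever replaced it. In an open-label trial one would also not want post-switch scores to be kept or dropped by a choice made late.

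**Working it through.** **What the text implies.** Put side by side, 5.4, 6.4, 8.1, 17.2 and 17.4.1.1 leave one plain reading: a score given at week 32 or 51 is used, under the randomised arm, whatever the subject is then taking. The discontinuation-visit score belongs to neither scheduled time, so it does not enter a model defined for weeks 32 and 52; 17.5 still has it reported.

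**Inputs.** From 17.1: 45 and 15 subjects, with no formal sample-size calculation, so there is no planned power to reproduce. The documents give no stopping or switching rate and no TSQM-9 SD.

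- Assumed number of somapacitan switchers, k: 1 to 3. The only expected-loss figure is under 7%, for missing CT scans in 17.4.1.1; 0.07 × 45 = 3.15. It is a benchmark, not a switching rate.
- Assumed gap d between the post-switch score and the score the subject would have given on trial product: 0.5 to 2 SD, either sign.

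**Standard error of the week-52 difference**, in SD units: √(1/45 + 1/15) = 0.298.

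**Shift from somapacitan switchers** = (k/45) × d.

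| k | d | Shift (SD) | Shift / SE |
|---|---|---|---|
| 1 | 0.5 | 0.011 | 0.04 |
| 1 | 2 | 0.044 | 0.15 |
| 3 | 0.5 | 0.033 | 0.11 |
| 3 | 1 | 0.067 | 0.22 |
| 3 | 2 | 0.133 | 0.45 |

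A shift of one full standard error needs k = 0.298 × 45 / d: about 13 switchers at 1 SD, or 7 at 2 SD.

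**Shift from Norditropin switchers.** One subject at 1 SD gives 1/15 = 0.067 SD, the same as 3/45. The smaller arm makes each switcher count three times as much, so there is no general reason to expect the effect mainly on the somapacitan side.

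**Direction.** A somapacitan subject who loses convenience by returning to daily injections lowers the somapacitan mean. One who was dissatisfied and recovers on another product raises it.

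**Would an on-treatment MMRM do better?** Take k = 3, a 1 SD gap, and as reference the score the subject would have given had they stayed on product. A simulation of 4,000 trials with a week 32–52 correlation of 0.6 gave these biases:

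| Case | As randomised | On-treatment |
|---|---|---|
| Convenience lost after switch | −0.07 | 0.00 |
| Dissatisfied on drug, recovers; switch after week 32 | +0.07 | +0.03 |
| Dissatisfied on drug, recovers; switch before week 32 | +0.07 | +0.07 |

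Hand arithmetic agrees. If the switch comes before week 32, the subject's scheduled scores all drop out, and the missing deficit is 3/45 × 1 = 0.067. If it comes after, the week-32 score predicts a fraction r of the week-52 deficit, which leaves 0.067 × (1 − r): 0.027 at r = 0.6, about 0.047 at r = 0.3 and 0.013 at r = 0.8 (simulated 0.027, 0.046 and 0.013). The alternative model helps in one case, partly in another, and not at all for early dissatisfied stoppers.

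**The follow-up visit.** A related worry is that 8.1 keeps early stoppers on the flow chart and also says "The follow-up visit (week 53) must be performed at least two weeks after last administration of somapacitan", with 8 days for Norditropin. These are minimum intervals, and they match a completer's own schedule in 5.3. The last weekly dose at week 51 is 14 days before week 53; the last daily dose on day 6 of week 51 is 14 − 6 = 8 days before. Someone who stopped earlier and attends at week 53 exceeds both. The statements are compatible, and they concern antibody sampling, not TSQM-9.

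**The case for a change.** The strongest argument for a change is that a treatment-policy analysis fits poorly with a questionnaire about one product. It answers how satisfied subjects assigned to somapacitan are with whatever they take at week 52, while 4.1 asks about somapacitan. Section 3.1.4 reports that weekly dosing was found more convenient than daily, so the convenience score is the one most exposed. Section 17.2 lets observations be excluded before lock without a stated criterion, and the SAP is optional. A supplementary model costs little: excluding 3 of 45 inflates the standard error by √(1/42 + 1/15) / 0.298 = 1.009.

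Part of this stands. The plan never names its approach, and it does not say which product a switched subject rates; the written questionnaire instructions are not in the documents, so even the claim that another product is rated is only probable. But analysis as randomised with continued follow-up is coherent, and nobody proposes to replace it. The extra model would be a second view of a supportive endpoint, and it fails for the subjects whose dissatisfaction made them stop early. Borrowing the 14-day limit from 17.3 has no stated rationale for a satisfaction score. The power to exclude observations requires signed reasons before lock, so a departure from the default would be on record.

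**Conclusion.** No change is needed. The plan does determine what happens to a post-switch TSQM-9 score: it is analysed under the randomised arm. That is a legitimate policy left unnamed, and analysts following 17.2 and 17.4.1.1 would apply it without difficulty. They would also report how many subjects changed product and when, which is what a reader needs to interpret the score.

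Under the assumed 1 to 3 somapacitan switchers and gaps of 0.5 to 2 SD, the shift is 0.01 to 0.13 SD, no more than 0.45 standard errors, of uncertain sign and possible from either arm. The primary safety endpoint is untouched. The conclusion rests on switching being uncommon, which the documents neither state nor rule out. About 7 to 13 of the 45 somapacitan subjects would have to switch, all with gaps of 2 or 1 SD in the same direction, for the shift to reach one standard error. Switching on that scale would be visible in the disposition data, and the TSQM-9 result would then be read accordingly.
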